### *Primary outcome*

The percentage of patients reporting pain equivalent to an NRS score > 3 after 6 months

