## Background

In Denmark, around 12,700 patients undergo cesarean delivery (CD) annually, constituting approximately 20% of all childbirths in the country (Danish Birth Registry 2023). Worldwide, the number is increasing yearly with more than 20 million CDs performed annually (Betran et al. 2021).

Postoperative pain after CD is typically moderate to severe in intensity and still constitutes a significant challenge, balancing effective pain relief and potential side effects ([name], [name] and [name] 2023; Lindelof et al. 2022; Roofthooft et al. 2021). Correlations between moderate to severe acute pain and the development of persistent pain after CD is still unclear (Eisenach et al. 2008; Nikolajsen et al. 2004; Sun and Pan 2019; Yimer and Woldie 2019).

Persistent pain is observed after various surgical procedures, posing a challenge for many patients (Kehlet, Jensen, and Woolf 2006). The reported incidence of persistent pain after CD varies considerably among studies; in a review of persistent pain after CD (Sun and Pan 2019) 11-27% of patients reported pain after six months. Four Danish studies have addressed acute pain following CD in the Danish population ([name],

[name], and [name] 2023; Hansen et al. 2019; Lindelof et al. 2022; Nikolajsen et al. 2004). One of these studies has also examined the occurrence of persistent pain (Nikolajsen et al. 2004); in a single-center study including 220 patients with a mean follow-up time of 10.2 months (range 6-17.6). Nikolajsen et al. concluded that 5.9% of the patients experienced pain from the cesarean scar area, daily or almost daily. To our knowledge, no studies have prospectively explored the potential effects of postoperative pain on functional outcomes and the ability to care for the infant beyond the early postoperative period.

Both pre-, intra-, and postoperative factors have been associated with an increased risk of persistent pain after surgery (Kehlet, Jensen, and Woolf 2006; Sun and Pan 2019). Current approaches to persistent pain prevention aim to use surgical techniques that avoid nerve damage, reduce tissue injury, optimize multimodal analgesia, and reduce acute postoperative pain (Kehlet, Jensen, and Woolf 2006; Sun and Pan 2019, Tan et al. 2022). The current predominance of evidence emphasizes an association between the severity of acute pain after surgery and the development of persistent pain (Yimer and Woldie 2019).

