### *Secondary outcomes*

1. Severe pain during the last 24 hours. NRS 0-10
2. Pain at rest during the last 24 hours. NRS 0-10
3. Use of analgesic medication in the past week due to pain (Paracetamol, Non-Steroidal Anti-Inflammatory Drug, opioid). Yes/No. What kind.
4. Pain's affect on daily activities. 1-5: Not at all, a little, to some extent, to a great extent, cannot do due to pain.
5. Pain's affect on engaging in strenuous physical activity. 1-6: Not at all, a little, to some extent, to a great extent, cannot do due to pain, I don't know - I haven't tried.
6. Pain's affect on meeting the infant's needs. 1-5: Not at all, a little, to some extent, to a great extent, cannot do due to pain.
7. Pain's affect on sleep. 1-4: Not at all, a little, to some extent, to a great extent.
8. Pain's affect on mood. 1-4: Not at all, a little, to some extent, to a great extent.
9. Pain/discomfort when sitting down or standing up from a chair. 1-5: Not at all, a little, to some extent, to a great extent, cannot do due to pain.
10. Pain/discomfort when walking on stairs. 1-5: Not at all, a little, to some extent, to a great extent, cannot do due to pain.

11. Pain/discomfort when getting in or out of bed. 1-5: Not at all, a little, to some extent, to a great extent, cannot do due to pain.
12. Pain/discomfort when carrying the infant. 1-5: Not at all, a little, to some extent, to a great extent, cannot do due to pain.
13. Pain/discomfort when sitting up for less than 30 minutes. 1-5: Not at all, a little, to some extent, to a great extent, cannot do due to pain.
14. Pain/discomfort if sitting up for more than 30 minutes. 1-6: Not at all, a little, to some extent, to a great extent, cannot do due to pain, I don't know - I haven't tried.
15. Pain/discomfort when moving around at home. 1-5: Not at all, a little, to some extent, to a great extent, cannot do due to pain.
16. Pain/discomfort if walking for more than 30 minutes. 1-6: Not at all, a little, to some extent, to a great extent, cannot do due to pain, I don't know - I haven't tried.
17. Pain/discomfort when bending down. 1-5: Not at all, a little, to some extent, to a great extent, cannot do due to pain.
18. Pain/discomfort during or after sexual intercourse. 1-7: Not at all, a little, to some extent, to a great extent, cannot do due to pain, I don't know - I haven't tried, I prefer not to answer.

Neuropathic pain (Andersen et al. 2019):

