#### *Exploratory outcomes*

1. Recall of acute pain at 12 and 24 hours after CD. Asked 12 months after CD.
2. Percentage of patients experiencing pain with an NRS > 3 at 1, 2, 3, and 12 months, as well as 2, 3, 4, and 5 years after CD.
3. Association between severe acute pain (NRS > 6) during the first 24 hours and the occurrence of persistent pain at 6 and 12 months after CD.
4. Prevalence of chronic pain before pregnancy.
5. Prevalence of chronic pain before pregnancy and its association with the development of persistent pain at 6 and 12 months, and 2, 3, 4, 5 years after CD.
6. Association between uterine exteriorization versus in situ repair in CD and the occurrence of persistent pain at 6 and 12 months, as well as 2, 3, 4, and 5 years after CD.

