## Development and validation of questions

PROMs are collected through SMS-based questionnaires. The questionnaires were developed with inspiration from studies on chronic pain (Kehlet 2006) and studies specific for the CD population (Eisenach et al. 2008; Nikolajsen et al. 2004; Sun and Pan 2019; Yimer and Woldie 2019). The Numeric Rating Scale (NRS) 0-10 was employed for pain assessment (Eisenach et al. 2008) and a 1-5/6 scale was utilized for PROMs related to function.

As part of the process of developing the questionnaires, we sought input from patients, anesthetists, and obstetricians to identify key areas relevant to representing recovery and pain in the months and years after CD, and we conducted five structured interviews with CD patients 3–6 months post-surgery. Subsequently, questions were developed and tested using standardized survey design methods (Duffett et al. 2011; Eysenbach 2004). The questionnaires underwent initial testing on professionals and the same five CD patients who had participated in the interviews. Adjustments were made based on this feedback. The questionnaires were then re-tested on both professionals and the five CD patients, with no further adjustments needed. Following this, the questionnaires were programmed into the web-based REDCap database (Research Electronic Data Capture) (Harris et al. 2009) and optimized for presentation on smartphone screens. Finally, the questionnaires were set-up to be sent out as an SMS via an external server (Sure-SMS, Denmark) with links to the questionnaires in REDCap. The questionnaires sent at various time points consist of 23 short questions, that can be answered on the phone in less than 5 minutes.

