## Appendix 1-8

1. Project approval from the research lawyer at The Capital Region (Region Hovedstaden) Center for Data Notifications. Approval number P-2023-90.
2. Ethical approval assessment, journal number F-23004686.
- 3-6. Data agreements for research projects between the regions.
7. Collaboration agreement.
8. Overview of the questions that are set up as questionnaires in REDCap and sent to the patient via a link in SMS.

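### Does the label ‘severe pain’ on the first NRS item stop it from supplying a primary outcome set at NRS > 3?

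*Protocol*

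**What the plan says.** The Primary outcome section gives a threshold and a time point: "The percentage of patients reporting pain equivalent to an NRS score > 3 after 6 months". It names no questionnaire item, no activity state and no recall window.

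Two entries under Secondary outcomes are rated on the NRS. Item 1 is "Severe pain during the last 24 hours. NRS 0-10" and item 2 is "Pain at rest during the last 24 hours. NRS 0-10". The remaining items are Yes/No or ordinal, and Development and validation of questions says that "a 1-5/6 scale was utilized for PROMs related to function".

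The word *severe* also appears in two other relevant places. The Background says "Postoperative pain after CD is typically moderate to severe in intensity". The Exploratory outcomes section gives it a number: "Association between severe acute pain (NRS > 6) during the first 24 hours". The same section reuses the primary threshold at other times: "Percentage of patients experiencing pain with an NRS > 3 at 1, 2, 3, and 12 months".

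The questions as sent to patients are in Appendix 8, listed as "Overview of the questions that are set up as questionnaires in REDCap". That appendix is not in the text at hand.

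**The concern.** The primary outcome has to come from one of the two NRS items. Item 2 covers rest only, so item 1 is the natural candidate, yet its label names a grade of pain. If *severe* carries the meaning it has for acute pain (NRS > 6), the label and the cut-off of > 3 pull apart. A patient with moderate pain on movement and little at rest might answer 0 or a low number to a question about severe pain. The ordinal activity items would not recover an NRS score for her.

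At stake is the study's main result. If item 1 asks for the worst pain of the last day, the 6-month percentage is the prevalence of at least moderate pain. If it asks only about severe pain, the percentage drifts down towards the prevalence of severe pain. The same doubt would carry over to the other time points in exploratory outcome 2.

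**Working it through.** No sample-size or power figure bears on this point, so the check sets the sections side by side, with simple counts.

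1. **Which items could supply the outcome.** Development and validation of questions says each questionnaire has 23 questions. Secondary outcomes lists 18 items plus 5 neuropathic items, 18 + 5 = 23. No separate primary-outcome question is apparent. Two of the 23 use the NRS and 23 − 2 = 21 do not. The outcome therefore comes from item 1 or item 2.

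2. **Whether item 1 can record scores of 4 to 6.** It is scored 0-10, and the protocol states no floor, filter or skip rule. Scores above 3 are 4 to 10, which is 7 values. Scores above 6 are 7 to 10, which is 4 values. The values between the two cut-offs are 7 − 4 = 3 (4, 5 and 6), and all three can be entered. A percentage above 3 can be computed directly. The count of 3 concerns points on a scale and says nothing about how many patients would be affected.

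3. **Whether the label can mean only pain above 6.** A 0-10 scale has 11 values. If only scores above 6 were meaningful, 11 − 4 = 7 of them (0 to 6) would have no use. The reading that fits label and scale together is a rating of how severe the pain was, or of the worst pain.

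4. **Where the > 6 cut-off belongs.** It defines an exposure group, severe acute pain in the first 24 hours after delivery, for an association with later pain. Item 1 is a raw rating weeks to years later and carries no cut-off. The Background sentence describes postoperative pain in general and defines nothing.

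5. **Which item the primary outcome implies.** The primary outcome is not limited to rest, and item 2 is. Item 1 is therefore the one that matches. If item 1 is worst pain (an assumption), any patient who answers consistently scores at least as high on item 1 as on item 2. The percentage above 3 on item 1 is then at least that on item 2. The gap cannot be sized from the protocol. Both items refer to the last 24 hours, so the recall window is the same whichever is used.

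6. **What a rewrite would alter.** Matching the label to Appendix 8 and adding cross-references would leave the questions, the answers and the computed percentage from a given item as they are.

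**The case for a change.** The strongest reply is that a number which can be computed is not thereby defined. The same column of data would estimate one prevalence if patients were asked for their worst pain and another if they were asked about severe pain, and no analysis plan can repair answers to a differently worded question. An unnamed source item also leaves room to choose between items 1 and 2 after the data are seen. The correction would cost only a few words.

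Part of this stands. The label is loose, the source item is not named, and the two items could give different percentages. A request for clarification would be reasonable.

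The rest does not carry. The feared under-reporting depends on the wording patients read. Participants must speak and read Danish, so the English label in the protocol is presumably not that wording, and Appendix 8 is not shown. The questionnaires were tested on professionals and five patients, adjusted, and tested again without further changes. That does not prove the item is clear, but nothing in the protocol points to misreading. If the Danish question were faulty, relabelling the protocol would not mend it.

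The room for choosing an item is limited. Both items are listed outcomes, so a report of the listed outcomes would show both. The planned analysis is descriptive, with a convenience sample and no stated significance level or power target that the choice could disturb. Naming the source item of a derived percentage is also commonly left to the statistical analysis plan, which is not at hand.

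**Conclusion.** The concern does not call for a change. Item 1 can supply the NRS > 3 percentage, and the > 6 cut-off for acute pain does not govern it. What is left is an imprecise label and a missing cross-reference, a gap that an analyst would fill sensibly by taking the item not restricted to rest and saying so in the report.

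The effect on the 6-month percentage cannot be estimated from the protocol, and no stated rule is shown to give a wrong result. The conclusion rests on two assumptions: that item 1 is meant as a rating of worst or overall pain severity, and that the Danish question in Appendix 8 says so. If Appendix 8 showed a question confined to severe pain, the matter would concern the questionnaire itself and how its result is described, and it would need a fresh look.

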### *Secondary outcomes*

1. Severe pain during the last 24 hours. NRS 0-10
2. Pain at rest during the last 24 hours. NRS 0-10
3. Use of analgesic medication in the past week due to pain (Paracetamol, Non-Steroidal Anti-Inflammatory Drug, opioid). Yes/No. What kind.
4. Pain's affect on daily activities. 1-5: Not at all, a little, to some extent, to a great extent, cannot do due to pain.
5. Pain's affect on engaging in strenuous physical activity. 1-6: Not at all, a little, to some extent, to a great extent, cannot do due to pain, I don't know - I haven't tried.
6. Pain's affect on meeting the infant's needs. 1-5: Not at all, a little, to some extent, to a great extent, cannot do due to pain.
7. Pain's affect on sleep. 1-4: Not at all, a little, to some extent, to a great extent.
8. Pain's affect on mood. 1-4: Not at all, a little, to some extent, to a great extent.
9. Pain/discomfort when sitting down or standing up from a chair. 1-5: Not at all, a little, to some extent, to a great extent, cannot do due to pain.
10. Pain/discomfort when walking on stairs. 1-5: Not at all, a little, to some extent, to a great extent, cannot do due to pain.

11. Pain/discomfort when getting in or out of bed. 1-5: Not at all, a little, to some extent, to a great extent, cannot do due to pain.
12. Pain/discomfort when carrying the infant. 1-5: Not at all, a little, to some extent, to a great extent, cannot do due to pain.
13. Pain/discomfort when sitting up for less than 30 minutes. 1-5: Not at all, a little, to some extent, to a great extent, cannot do due to pain.
14. Pain/discomfort if sitting up for more than 30 minutes. 1-6: Not at all, a little, to some extent, to a great extent, cannot do due to pain, I don't know - I haven't tried.
15. Pain/discomfort when moving around at home. 1-5: Not at all, a little, to some extent, to a great extent, cannot do due to pain.
16. Pain/discomfort if walking for more than 30 minutes. 1-6: Not at all, a little, to some extent, to a great extent, cannot do due to pain, I don't know - I haven't tried.
17. Pain/discomfort when bending down. 1-5: Not at all, a little, to some extent, to a great extent, cannot do due to pain.
18. Pain/discomfort during or after sexual intercourse. 1-7: Not at all, a little, to some extent, to a great extent, cannot do due to pain, I don't know - I haven't tried, I prefer not to answer.

Neuropathic pain (Andersen et al. 2019):

19. Pins and needles, tingling or stabbing sensations in or around the area of the surgery? Yes/No
20. Electric shock like sensation or jabbing feelings in the skin area in or around the area of the surgery? Yes/No
21. Heat or burning sensations in or around the area of the surgery? Yes/No
22. Pain caused by the lightest of touches in or around the area of the surgery? Yes/No
23. Pain caused by cold temperatures in or around the area of surgery? Yes/No

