## Outcomes

All outcomes related to **pain**, refer to pain in or around the surgical area. Assessments are conducted at 5 weeks, 2, 3, 6, and 12 months, and after that every 6 months until 3 years after surgery.

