## Data collection

The questionnaires are sent at fixed time intervals: at 5 weeks, 2 months, 3 months, 6 months, and 12 months, and thereafter every 6 months until 5 years after CD. Reminders are sent the day after the initial questionnaire in case of no response. All questionnaire data are entered directly into the closed and secure system REDCap. Data from journal entries are also entered into REDCap. At all hospitals, a data manager can retrieve data for the patients included in the project. The primary investigator holds the overall responsibility for the data.

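### The two infant-care items have no 'not relevant' answer, so their results after about 12 months, mainly for carrying the infant, become ambiguous

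*Protocol*

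**What the plan says.** Two of the 23 secondary outcomes concern care of the child. Item 6 reads "Pain's affect on meeting the infant's needs. 1-5: Not at all, a little, to some extent, to a great extent, cannot do due to pain". Item 12 reads "Pain/discomfort when carrying the infant. 1-5: Not at all, a little, to some extent, to a great extent, cannot do due to pain". Both lists stop at the fifth answer. Items 5, 14, 16 and 18 each add an answer for women who do not know because they have not tried the activity, and item 18 also lets a woman decline to answer.

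The Outcomes section sets one schedule for the assessments: 5 weeks, 2, 3, 6 and 12 months, and "after that every 6 months until 3 years after surgery". The Data collection section gives the same early rounds but continues "thereafter every 6 months until 5 years after CD". Under Development and validation of questions, the protocol states: "The questionnaires sent at various time points consist of 23 short questions". It describes no dropping or rewording of items in later rounds. The questionnaires themselves are in Appendix 8, which is listed as "Overview of the questions that are set up as questionnaires in REDCap and sent to the patient via a link in SMS" but is not reproduced.

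**The concern.** The Background says that, to the authors' knowledge, no study has prospectively explored how postoperative pain affects function and the ability to care for the infant beyond the early postoperative period. Items 6 and 12 are the only two of the 23 secondary items that address this directly.

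Both are tied to a stage of the child's life that ends during follow-up. At 2 to 5 years the child is no longer an infant and may seldom be carried. A woman in that position has no answer that fits. If she chooses 'Not at all', her record looks the same as that of a woman who carries her child without pain. If she leaves the item blank, the reason for the blank is not recorded. The wording also does not say which child is meant if she has since had another.

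This has to be settled in the instrument. Once the answers are collected without the distinction, no later analysis can recover it.

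**Working it through.** The protocol gives no figure for this point, so there is none to reproduce. The check has three parts.

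**1. Which items have a way out**

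| Items | Answers | 'Haven't tried' answer |
|---|---|---|
| 5, 14, 16 | 1-6 | yes |
| 18 | 1-7 | yes |
| 6 and 12 (infant care) | 1-5 | no |
| 4, 9, 10, 11, 13, 15, 17 (daily activities and movements) | 1-5 | no |

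The activities in the last row remain part of daily life throughout follow-up. Items 6 and 12 are the ones whose applicability can be expected to change with the child's age.

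**2. How many rounds fall after 12 months**

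- Rounds up to month 12: 5 weeks, 2, 3, 6 and 12 months = 5.
- End at 3 years (Outcomes): months 18, 24, 30 and 36 = 4 more. Total 9; share after month 12 = 4/9 = 44%.
- End at 5 years (Data collection): months 18 to 60 in steps of 6 = 8 more. Total 13; share after month 12 = 8/13 = 62%.

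**3. What an item that no longer applies could do to the reported percentage**

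Let p be the share with any pain among women to whom the item still applies, and q the share of women to whom it does not. The protocol gives neither, so both are assumed here: p = 10%, and q = 25%, 50% or 75%. The reported share depends on what the second group does:

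- all answer 'Not at all': p(1 - q)
- all leave the item blank: p, among those who answer
- all answer 'cannot do due to pain': p(1 - q) + q

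| q (assumed) | 'Not at all' | Blank | 'Cannot do due to pain' |
|---|---|---|---|
| 25% | 0.10 x 0.75 = 7.5% | 10% | 7.5% + 25% = 32.5% |
| 50% | 0.10 x 0.50 = 5.0% | 10% | 5.0% + 50% = 55.0% |
| 75% | 0.10 x 0.25 = 2.5% | 10% | 2.5% + 75% = 77.5% |

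These are illustrations and not estimates. They show that the late figure depends on how women handle a question that does not fit, which the protocol does not address. If a 'not relevant' answer is available, used as intended and taken out of the denominator, the reported share is p = 10% at every q.

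**The case against.** **Is the item set really the same in late rounds?** The Secondary outcomes section lists outcomes, possibly with short labels, and Appendix 8 is not available. Content does vary somewhat by round: recall of acute pain is asked at 12 months, and the question about continuing is asked at 12 months and 2, 3 and 4 years. This stands as a limit. A constant set of 23 items is the natural reading, but it cannot be confirmed.

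**Are late answers pushed toward 'Not at all'?** A reader might infer this, and with it a spurious decline in pain interference over time. The document does not support it. Nothing says that answers are mandatory, so a woman may skip the item, and the illustration above moves down, not at all, or up depending on the assumed behaviour. Multiplying assumed shares only restates the assumption.

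**Are late results uninterpretable?** That is also too strong. Item 6 stays largely answerable: a woman whose pain does not interfere with meeting her child's needs can truthfully say so at any age of the child. The infant is most naturally the child of this cesarean, and the pain asked about is in or around the surgical area. The difficulty lies mainly in item 12.

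**Is the lack of a way out inconsistent?** The existing opt-out is attached mostly to demanding or optional activities, and other routine activities have none, so the sponsor may have followed a coherent rule. That is fair, but the rule does not allow for an activity that fades with time. The described testing, on five women interviewed 3 to 6 months after surgery, was not placed to show this.

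**Can it wait for an analysis plan?** The choice of denominator could. The missing answer option cannot, and the planned accounting for the amount of missing data does not supply the reason for a blank.

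**Conclusion.** As listed, items 6 and 12 offer no answer for a woman to whom the question no longer applies, and the protocol applies them at every round to year 3 or year 5. After about 12 months their results become ambiguous, chiefly those of item 12. The direction and size of any distortion are unknown. The conclusion assumes that the questionnaires in Appendix 8 follow the listed items without late changes.

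The reach is limited. It covers 2 of 23 secondary items in a descriptive study, at 4 of 9 or 8 of 13 rounds. The primary outcome, NRS above 3 at 6 months, is untouched, and no exploratory outcome uses these items. The five rounds to 12 months are essentially unaffected and already describe infant care beyond the early postoperative period. This is a worthwhile refinement and does not threaten the study's main results. The 3-year versus 5-year end of follow-up is a separate contradiction to be reconciled; the point holds under either schedule.

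**What to change.** First check Appendix 8. If the late questionnaires already handle this, say so in the Secondary outcomes section and nothing more is needed. If they do not, then for questionnaires not yet sent:

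- add a 'not relevant / do not do this' answer to items 6 and 12, kept separate from 'cannot do due to pain';
- word both items to refer to the child born at this cesarean;
- report the percentage at each time point among women to whom the item applies, with the number for whom it does not.

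Alternatively, state in the protocol that these two outcomes are restricted to time points up to 12 months. No late wording is then needed, and the late questionnaires lose two questions.

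The cost is an edit to two REDCap items and a line or two in the protocol. The downside is a small difference in item format between early and late rounds, to be noted wherever the two are compared. Because inclusion was spread from 01.11.2023 to 30.07.2024, it is preferable to introduce the change at a fixed time point that no woman has yet reached, so that all women answer the same version at a given round.
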